Subjects randomized to the treatment arm will receive enoxaparin adjusted to the target anti-Xa activity. Subjects randomized to the control arm will not receive placebo because of ethical concerns of inducing pain with subcutaneous administration without any potential for direct benefit. All subjects in the study will undergo the remaining study procedures.

TREATMENT REGIMEN WITH ENOXAPARIN

The 1st dose of enoxaparin be given <24 hours after insertion of the CVC. The initial dose will be 0.75 mg/kg for children ≤2 months old or 0.5 mg/kg (maximum of 30 mg) for older children (Table 1). The initial dose will be doubled in obese children (refer to Appendix I and II) and halved in children with renal insufficiency (estimated creatinine clearance calculated by the Schwartz equation $<75 \text{ mL/min/1.73 m}^2$).⁴⁹ The clinical nurse will give enoxaparin subcutaneously every 12±2 hours after the first dose until removal of the CVC, or earlier upon discharge from the ICU, radiologic diagnosis of CADVT, start of therapeutic anticoagulation, clinically relevant bleeding develops, HIT is diagnosed, or 28 days after insertion of the CVC.

Administration

Route. Enoxaparin is to be administered by subcutaneous route per local site clinical procedures.

Site. In children <10 kg or <1 year of age, the thigh is the preferred site of administration. Alternate between the left and right thigh. In children ≥10 kg or ≥1 year of age, the abdomen is the preferred site. For children who do not have sufficient subcutaneous tissue in the abdomen, the anterolateral thigh may be used as secondary site for administration.

Table 1: Initial dose

Age	Drug	Dose/ Potency*	Dose Frequency	Route	Regimen/ Treatment Period†	Use
Children ≤2 mos.	Enoxaparin	0.75 mg/kg	Q12 hours	Subcutaneous	Until CVC is removed	Experimental
Children >2 mos.	Enoxaparin	0.5 mg/kg (maximum of 30 mg)	Q12 hours	Subcutaneous	Until CVC is removed	Experimental

*The initial dose will be doubled in obese children (refer to Appendix I and II) and halved in children with renal insufficiency (estimated creatinine clearance calculated by the Schwartz equation $<75 \text{ mL/min/1.73 m}^2$).⁴⁹ †Enoxaparin treatment will stop before the CVC is removed upon discharge from the ICU, radiologic diagnosis of CADVT, start of therapeutic anticoagulation, clinically relevant bleed develops, HIT is diagnosed, or 28 days after insertion of the CVC, whichever comes first.

Titration dose

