The dose of enoxaparin will be adjusted to a target anti-Xa activity of 0.2-0.5 IU/mL.^{23, 46, 47} The target anti-Xa activity is a peak level and, therefore, timing is extremely important. The peak level must be drawn 4-6 hours after the dose is actually administered. If the child has other labs ordered which are not time dependent, the other labs should be drawn at the same time the enoxaparin peak level is needed.

Using standard methods, anti-Xa activity will be measured 4-6 hours after a dose at the following time points:

1. After the first 3 doses. If needed, the dose will be adjusted to achieve the target anti-Xa activity. See Table 2 for dose titration.
2. After the 3rd dose of a dose titration until the target anti-Xa activity is reached. Once the anti-Xa activity is within target, the dose will be maintained. See Table 2 for dose titration.
3. Weekly to ensure adequate dosing. Similar dose titration as listed in Table 2 will be done to achieve adequate dosing.

Table 2: Enoxaparin Dosage Titration

Anti-Xa Activity	Enoxaparin Dose Titration	Next Anti-Xa Activity Check
<0.10 IU/mL	Increase dose by 20%	After 3 rd dose.
0.10-0.19 IU/mL	Increase dose by 10%	After 3 rd dose.
0.20-0.50 IU/mL	Keep same dosage	Weekly
0.51-1.00 IU/mL	Decrease dose by 10%	After 3 rd dose.
>1.00 IU/mL	Hold all doses until anti-Xa is 0.3, IU/mL, then decrease dose by 20%	Before next dose and every 12 hours, until anti-Xa <0.3 IU/mL

(Modified from Monagle P, et al. *Chest*, 2001, 119:344S)⁵⁰

Discontinuing enoxaparin

The child will be removed from the study and Enoxaparin will be discontinued for the purposes of the study if ANY the following occur:

1. A clinically relevant bleeding event
 - a. Drop in Hb of ≥ 2 g/dl in 24 hours
 - b. Blood product transfused for the bleeding event
 - c. Required medical or surgical intervention to restore hemostasis
 - d. In a critical organ (*i.e.*, retroperitoneum, pulmonary, intracranial or central nervous system)
2. HIT is diagnosed (*i.e.*, positive serotonin release assay)

Holding the Dose

Enoxaparin will be stopped temporarily if ANY the following occur

1. Coagulopathy (*i.e.*, international normalized ratio >2.0, activated partial thromboplastin time >50 seconds or platelet count <50,000/mm³) develops

2. 12 hours before surgery or invasive procedure
3. In cases of suspected HIT (*i.e.*, an unexplained decrease in platelet count $<50,000/\text{mm}^3$ or by 50% of baseline value in the ICU).

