APPENDIX II

DOSE CALCULATION WORKSHEET

Subject #:	Subject Name:	Subject MRN:
Age:	Weight (kg):	Height (cm):
Date:	Dose Sequence: (e.g. 1-3, 4-6, etc)	BMI (only applicable for age 2-18)
	kg	cm
		kg/m ²

SECTION I					
Instructions for initial dose (#1-3), otherwise skip to Section II					
1. Using the table below, select dose for patient based on patient's age: _____ mg/kg					
Age	Drug	Dose/Potency	Dose Frequency	Route	Regimen/ Treatment Period
Children ≤2 months	Enoxaparin	0.75 mg/kg	Every 12 hours	Subcutaneous	Until CVC is removed
Children > 2 months	Enoxaparin	0.5 mg/kg (maximum of 30 mg)	Every 12 hours	Subcutaneous	Until CVC is removed
2. Evaluate patient's characteristics for dose modification.					
a. For subject between the ages of 0 to 2 years old, does the weight for the corresponding height exceed the 95th percentiles weight provided in Appendix II? _____ Yes _____ No					
• If yes, double the dose due to obesity					
b. For subject between the age of 2 to 18 years old, does the BMI for the corresponding age exceed the 95th percentiles BMI provided in Appendix III? _____ Yes _____ No					
• BMI = (Weight (in kilograms)/Height (in meters ²))					
_____ kg/m ² = (_____ kg / (_____ m) ²)					
• If yes, dose is doubled due to obesity.					
3. Based on patient's age and obesity status, input dose into Section II under "mg/kg Dose Selected"					

SECTION II		
mg/kg Dose Selected	Serum Creatinine	Anti-Xa Activity
mg/kg	mg/dL	IU/mL
Step 1: Renal function		

 Determine the subject's k constant: 
 k is 0.33 in premature infants through the first year of life k is 0.43 for term infants through the first year of life k is 0.55 in boys age 2-12 years old and girls of any age k is 0.70 in adolescent boys over the age of 12 Calculate Glomerular Filtration Rate using Schwartz Equation: $GFR = k * Height (cm) / SCr (mg/dL)$ 		
_____ mL/min/1.73m ² = (_____ x _____ cm) / (_____ mg/dL)		
Using the Schwartz equation, is GFR less than 75 mL/min/1.73 m ² ? _____ Yes _____ No		
• If yes, halved the dose selected from Section I due to renal insufficiency.		
What is the current dose based on renal function? _____ mg/kg		
Step 2: Dose Calculation (1st Dose)		
Take the dose (mg/kg) determined in step 1 and multiply it by the patient's weight (kg)		
_____ mg (maximum of 30mg) = _____ mg/kg (dose) x _____ kg (weight)		
Step 3: Dose Titration (Subsequent Doses)		

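### The dosing instructions conflict on whether titrated doses are capped, leave the order of cap and modifiers unstated, and give a k list that overlaps for infant girls and is missing for boys aged 1 to <2 years

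*Combined protocol and SAP*

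**What the plan says.** **Starting dose.** Under Treatment Regimen with Enoxaparin, "The initial dose will be 0.75 mg/kg for children ≤2 months old", or "0.5 mg/kg (maximum of 30 mg) for older children (Table 1"). The text and the Table 1 footnote then modify it: "The initial dose will be doubled in obese children (refer to Appendix I and II"), and it is halved in renal insufficiency. Neither states whether the 30 mg maximum comes before or after the modification.

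**Titration.** "The dose of enoxaparin will be adjusted to a target anti-Xa activity of 0.2-0.5 IU/mL". Table 2 raises the dose by 20% when anti-Xa is below 0.10 IU/mL and by 10% at 0.10-0.19 IU/mL, repeated until the level is in range. That section gives no maximum.

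**Appendix II worksheet.** Obesity and renal function change the mg/kg dose, the result is multiplied by weight, and the cap comes last: "mg (maximum of 30mg") is printed on the first-dose line (Step 2) and again on the line for every later dose (Step 3). The renal step halves the dose if GFR, computed as k × height / creatinine, is below 75. Its k list includes "k is 0.43 for term infants through the first year of life" (0.33 if premature) and "k is 0.55 in boys age 2-12 years old and girls of any age". The last entry is 0.70 for boys over 12.

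**Status of the worksheet.** The Drug Dose section leaves dose calculation to local standards and calls the worksheet an example.

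**The concern.** These are instructions for an anticoagulant in critically ill children at six sites. If two pages of one protocol can be followed correctly and yield different doses, the intervention may vary by site and by the page consulted, and a safety review cannot easily tell a protocol deviation from a permitted reading.

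The trial's own outcomes are also exposed. The posterior probability that ETP at the second blood draw (D2) is below 700 nM·min informs the phase 3 dose. Time to target anti-Xa is a feasibility outcome, and the secondary analyses model ETP and anti-Xa over D1-D4 and look for predictors of reaching target. A cap that binds only in larger children, or a halving rule that is undefined for some infants and toddlers, would enter those analyses as an unrecorded difference in treatment.

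**Working it through.** The plan gives no worked dose, so there is no figure to reproduce. The rules are set side by side.

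**1. Cap during titration.** Inputs: Table 2 factors 1.2 and 1.1 with no maximum; worksheet Step 3, min(previous dose × factor, 30). A non-obese child of 60 kg or more starts at 0.5 × 60 = 30 mg.

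| Step from 30 mg | Table 2, +20% | Table 2, +10% | Worksheet |
|---|---|---|---|
| 1 | 36.0 | 33.0 | 30 |
| 2 | 43.2 | 36.3 | 30 |
| 3 | 51.8 | 39.9 | 30 |

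The first 20% step is cut short for non-obese children above 50 kg (0.5 × 50 × 1.2 = 30); at 55 kg it is 33 versus 30 mg. On the worksheet, an obese child is at the cap from the first dose at 30 kg (1.0 × 30 = 30).

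**2. k values.** Reading the first year as birth to the first birthday, a girl in that year matches 0.43 (or 0.33 if premature) and also 0.55. A boy from his first to his second birthday matches no entry, so his GFR cannot be computed from the list. The body gives no k.

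The dose is halved when k × height / creatinine < 75, that is, when creatinine > k × height / 75. Height and creatinine are not in the documents; assume a height of 60 cm:

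- k = 0.43: 0.43 × 60 / 75 = 0.344 mg/dL
- k = 0.55: 0.55 × 60 / 75 = 0.44 mg/dL

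The two values give opposite decisions for creatinine above 0.344 and up to 0.44 mg/dL. At an assumed 0.35 mg/dL, GFR is 0.43 × 60 / 0.35 = 73.7 (halve) or 0.55 × 60 / 0.35 = 94.3 (do not halve), a two-fold difference in dose.

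**3. Order of cap and modifier, children over 2 months.** Cap first: min(0.5 × weight, 30), then × 2 if obese or × 0.5 if renal insufficiency. Cap last (worksheet): min(0.5 × modifier × weight, 30).

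| Child | Weight (kg) | Cap first (mg) | Cap last (mg) | Ratio |
|---|---|---|---|---|
| Obese | up to 30 | equal | equal | 1.0 |
| Obese | 40 | 40 | 30 | 1.33 |
| Obese | 50 | 50 | 30 | 1.67 |
| Obese | ≥60 | 60 | 30 | 2.0 |
| Renal insufficiency, not obese | up to 60 | equal | equal | 1.0 |
| Renal insufficiency, not obese | 80 | 15 | 20 | 0.75 |
| Renal insufficiency, not obese | 100 | 15 | 25 | 0.60 |
| Renal insufficiency, not obese | ≥120 | 15 | 30 | 0.50 |

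With both modifiers or neither, the two orders agree at every weight. At 2 months or younger the cap is out of reach: even doubled to 1.5 mg/kg it would need 30 / 1.5 = 20 kg.

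**4. Which analyses are reached.** With doses every 12 hours, the third dose falls nominally 24 hours after the first and its anti-Xa draw at 24 + 4 to 24 + 6 = 28-30 hours. The first dose that draw could change is the fourth, at about 36 hours. D2 is taken 24±6 hours after D1 or with the anti-Xa draw, so it normally precedes any titrated dose. Items 2 and 3 act on the initial dose and can reach D2. Item 1 mainly affects time to target and the later ETP and anti-Xa data.

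**The case against.** Much of the case on the other side is fair.

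- **The body never prints a 60 mg dose.** A reader might infer that it states 60 mg where the worksheet states 30 mg. It does not: the doubling sentence refers to Appendix II, which caps last, and on that reading the starting doses agree at every weight. What stands is that the order is unstated and that cap-then-double is a natural reading of the sentence.
- **The maximum may be a general ceiling.** The Rationale for Dose Selection bases the maximum dose on adult approvals without restricting it to the first dose, so Table 2's silence could be an omission. But that remark follows a sentence on the starting dose, and elsewhere the body attaches 30 mg to the starting dose. The text does not settle it.
- **Anti-Xa-directed dosing is not made impossible.** That inference would go too far. Increases up to 30 mg, maintenance, reductions and holds all work on the worksheet, and some children may reach target at 30 mg. Only increases beyond 30 mg are blocked.
- **The Aim 2 decision is not undermined by the titration cap.** A reader might suppose it is, but D2 normally comes before any titrated dose.
- **The worksheet is only an example.** True, so it cannot by itself override Table 2. That status also lets sites resolve the gaps differently.
- **The infant values may be meant to take precedence for girls.** That would remove the overlap, but the list does not say so, and boys aged 1 to <2 years would still have no value.

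**Conclusion.** This is an internal inconsistency in the dosing instructions that needs correction, in three parts of unequal strength. The titration cap is a direct difference between Table 2 and worksheet Step 3 (36 versus 30 mg at the first 20% step from 30 mg) unless a general ceiling is read into the body. The k list, taken literally, has an overlap and a gap in a step that halves the dose. The order of cap and modifiers is unstated; it matters by up to two-fold, in either direction, only if the body is read as cap first.

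The first part reaches children at or near 30 mg with low anti-Xa. The third reaches only obese children above 30 kg, or non-obese children above 60 kg with renal insufficiency. The documents give no distribution of weight, obesity or creatinine, so the number affected among the roughly 50 of 100 children allocated to drug cannot be stated. That the intervention will differ between sites is a possibility the text leaves open, not something it establishes.

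**What to change.** The clinical and pharmacy leads should reconcile the Drug Dose and Rationale for Dose Selection sections, the treatment section with Tables 1 and 2, and Appendix II on three questions:

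1. Does the maximum apply before or after doubling or halving?
2. Does a maximum apply to titrated doses and, if so, where is it stated in the body?
3. Which single k applies to each age and sex, with no overlap or gap?

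All sites should then receive one consistent instruction, with the relation between the worksheet and local calculation standards made explicit. The worksheet's pointers can be corrected at the same time: it sends users to Appendices II and III for obesity tables that are in Appendix I. If children have already been dosed, the order and k used should be recorded for each so that the ETP and anti-Xa analyses can take account of it.

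The cost is a protocol clarification, a corrected worksheet and a training memo. No position is taken on which dose, cap or k is right.

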12 hours for children >2 months old.^{12, 23} The dose is adjusted to a target anti-Xa activity of 0.2-0.5 IU/mL.^{23, 46, 47} In the absence of prior trials in children, the same target anti-Xa activity recommended in adults will be used in this trial.²³ Among post-operative orthopedic patients on prophylactic dose of LMWH, the mean peak anti-Xa activity on Days 1, 3, 4 and 10 were 0.29, 0.25, 0.33 and 0.37 IU/mL. In acutely ill medical patients, the prophylactic dose of LMWH achieved anti-Xa activity of 0.21 to 0.41 IU/mL. Dose calculations are completed per local standards. An example dose calculation work sheet is provided in Appendix 2.

Rationale for Dose Selection/Regimen

The selection of doses to be used in this trial is based on commonly used doses for the drug.¹⁷ When prescribing enoxaparin in children as prophylaxis against DVT, the starting dose is typically 0.75 mg/kg for children ≤2 months old or 0.5 mg/kg (maximum of 30 mg) for older children. The present trial will utilize this dose as a starting point because of the proven tolerability in clinical care. The maximum dose is based on FDA-approved doses in adults. At these doses, enoxaparin has been shown to be safe without any significant increase in the risk of clinically relevant bleeding.⁴³

Reconstitution

Dilute Enoxaparin Sodium Injection, USP with sterile water for injection or normal saline. Draw up the appropriate dose in a polypropylene plastic tuberculin syringe sealed with a rubber tip cap.

Storage and Stability Requirements

Enoxaparin should not be stored above 25°C and should not be frozen.⁴⁵ When stored at 20°C to 22°C, enoxaparin, 1.2 mg/ml in normal saline, was stable for up to 48 hours. Enoxaparin when repackaged from commercial 0.3 mg syringes of enoxaparin, 100 mg/mL, into tuberculin syringes retained activity and sterility and remained pyrogen free for up to 10 days at 3°C. Undiluted enoxaparin lost activity within 2 days at 22°C. Enoxaparin diluted with sterile water for injection to 20 mg/ml, and stored at room temperature or under refrigeration, was stable for up to 4 weeks in glass or prefilled syringes, as measured by anti-Xa activity.

Handling

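### Obesity doubling and the 30 mg maximum: the dosing text read literally allows 60 mg from 60 kg, while the Appendix II worksheet, described only as an example, stops at 30 mg

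*Combined protocol and SAP*

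**What the plan says.** Five places bear on the point.

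- **Treatment Regimen with Enoxaparin, and Table 1 with its footnote.** The initial dose is 0.75 mg/kg up to 2 months of age and 0.5 mg/kg with a 30 mg maximum above that age. Then: "The initial dose will be doubled in obese children (refer to Appendix I and II". The dose is halved when estimated creatinine clearance is below 75 mL/min/1.73 m².
- **Appendix II worksheet.** Section I doubles the mg/kg figure for obesity. Section II Step 1 deals with renal function: "If yes, halved the dose selected from Section I due to renal insufficiency". Step 2 then reads "Take the dose (mg/kg) determined in step 1 and multiply it by the patient's weight (kg", with a 30 mg maximum printed on the product. Step 3 prints the same maximum on every titrated dose.
- **Drug Dose.** "Dose calculations are completed per local standards. An example dose calculation work sheet is provided in Appendix 2".
- **Rationale for Dose Selection/Regimen.** This discusses only the 0.5 and 0.75 mg/kg starting doses ("The present trial will utilize this dose as a starting point because of the proven tolerability in clinical care") and says of the cap: "The maximum dose is based on FDA-approved doses in adults". It does not mention doubling.
- **Titration dose and Table 2.** Doses move in 10% or 20% steps, and no maximum is stated there. After a change, the next level is taken as follows: "After the 3rd dose of a dose titration until the target anti-Xa activity is reached". Footnote c of the flow chart puts the first level 4-6 hours after the third dose.

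**The concern.** The body text and the worksheet put the cap and the doubling in opposite orders. In the body text the thing that is doubled is the initial dose, and that dose already carries its 30 mg limit. In the worksheet the limit comes last. A pharmacist who works from the regimen section or Table 1 can defend 60 mg for a 60 kg obese adolescent. A pharmacist who works from the worksheet dispenses 30 mg. The Drug Dose section permits either, because it makes the worksheet illustrative.

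At stake is an anticoagulant dose in critically ill children that may depend on the site. Three doses are given before any level is taken: 180 mg in total on one reading (3 × 60) and 90 mg on the other (3 × 30). The treatment arm would also contain two regimens in its heaviest children, and that split would follow site rather than design.

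**Working it through.** **Inputs.** Base dose 0.5 mg/kg, maximum 30 mg, children over 2 months (regimen section, Table 1). Obesity factor 2 and renal factor 0.5 (same places). Order of steps from Appendix II, Sections I and II. Let w be weight in kg.

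**Formulas, renal function not reduced.**

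- Body text read literally: 2 × min(30, 0.5w).
- Worksheet: min(30, 2 × 0.5w) = min(30, w).

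| Weight (kg) | Not obese (mg) | Obese, worksheet (mg) | Obese, literal text (mg) | Ratio |
|---|---|---|---|---|
| 20 | 10 | 20 | 20 | 1.00 |
| 30 | 15 | 30 | 30 | 1.00 |
| 40 | 20 | 30 | 40 | 1.33 |
| 50 | 25 | 30 | 50 | 1.67 |
| 60 | 30 | 30 | 60 | 2.00 |
| 80 | 30 | 30 | 60 | 2.00 |

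The readings part above 30 kg and reach the full twofold gap at 60 kg. Under the worksheet the doubling is complete up to 30 kg, partial from 30 to 60 kg, and absent from 60 kg.

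**Where there is no conflict.** In an obese child with clearance below 75, the literal text gives 0.5 × 2 × min(30, 0.5w) = min(30, 0.5w). The worksheet gives min(30, 0.5 × 2 × 0.5w), which is the same. At 2 months or younger the doubled dose is 1.5 mg/kg and would reach 30 mg only at 30/1.5 = 20 kg, so the cap does not matter.

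**Is 60 kg realistic?** Appendix I puts the 95th percentile BMI at 13.5 years at 25.62 for boys and 26.79 for girls. The height at which that BMI equals 60 kg is √(60/25.62) = 1.53 m and √(60/26.79) = 1.50 m. An obese child of that age above that height weighs more than 60 kg.

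**How many children?** The documents give neither an obesity rate nor a weight distribution. If 5-20% of the 50 treated children were obese (assumption), that is 2.5 to 10 children. Those over 30 kg without renal insufficiency would be fewer.

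**Side observation on step size.** Assume that the level is proportional to dose. A level p between 0.51 and 1.00 IU/mL needs the smallest n with p × 0.9ⁿ ≤ 0.50, at one cut per three doses (36 hours). From 0.60, n = 2, so the first in-target dose comes 3 days after dose 1. From 0.70, n = 4 (6 days). From 1.00, n = 7 (10.5 days). The background section gives mean catheterization as 6 days (SD 5).

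**The case against.** The best defence is that the order is settled. The doubling sentence itself sends the reader to Appendix II, where the cap is unmistakably last and is repeated for titrated doses. The rationale section ties the maximum to adult-approved doses, which points the same way. On this view 60 mg arises only if a site departs from the worksheet.

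Much of that stands. A reader might infer that the plan nowhere fixes the order, and that is not so: the rule exists and its intent is fairly clear. What the defence does not remove is that the Drug Dose section lets a site depart from the worksheet. Nor does it remove the conflict with the unqualified statement that the dose is doubled, when under the worksheet doubling has no effect from 60 kg. The titration section is also silent on any maximum.

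Stronger readings are tempting, and the documents do not support them:

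- **That obese children will overshoot the 0.2-0.5 IU/mL target.** The only peaks given for 1 mg/kg every 12 hours are adult (1.1-1.2 IU/mL). The background section itself warns against carrying adult data over to children. Whether obese children overshoot cannot be told from the documents.
- **That there is no quick way back from a high level.** Above 1.00 IU/mL, Table 2 holds all doses, checks every 12 hours and restarts 20% lower. The slow 10% steps apply only at 0.51-1.00.
- **That a level after dose 1 and an automatic return to the undoubled dose are needed.** The first is an extra procedure. The second would halve the dose on a reading as low as 0.51 in children up to 30 kg. With the cap last it also misfires in heavier children. From 60 kg the undoubled dose is the same 30 mg. Between 54 and 60 kg the step is smaller than Table 2's 10%, since 0.5w exceeds 27 mg. Above 48 kg a restart after a hold would be higher than Table 2's 80% (at 50 kg, 25 mg against 24 mg).
- **That Aim 2 needs a separate analysis without these children.** With 50 treated, SD 356, a flat prior and one to five such children averaging 300-500 nM·min (all assumptions), the dose decision changes only if the mean at the second draw lies between about 648 and 687.

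**Conclusion.** The body text and the worksheet conflict, and the Drug Dose section leaves the conflict open to local resolution. The size is up to twofold: no difference to 30 kg, 30 against 40 mg at 40 kg, 30 against 50 mg at 50 kg, and 30 against 60 mg from 60 kg. It is confined to obese children over 2 months and above 30 kg without renal halving. The dose figures rest on the documents alone. How many enrolled children fall in that group, and whether any site would read the text literally, are not known.

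The point calls for a clarification of an existing rule, not for a new one. It is worth making because the drug is an anticoagulant and the wording is easily settled. The pace of titration at 0.51-1.00 IU/mL in children on a doubled dose is an observation that the sponsor may wish to review. It is not a required change.

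**What to change.** 1. In the regimen section and the Table 1 footnote, state that the 30 mg maximum limits the final dose after obesity doubling and renal halving, and that it applies to initial and titrated doses alike.
2. In the Drug Dose section, make the Appendix II order of calculation mandatory. Local standards can still govern rounding and preparation.
3. While the worksheet is open, correct its pointers to the percentile tables. It sends users to Appendices II and III, but both tables are in Appendix I.

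The cost is a few sentences, with no added patients, samples or analyses. The sponsor should confirm one consequence: with the cap last, an obese child of 60 kg or more starts on the same 30 mg as a non-obese child and cannot be titrated above it. If doses above 30 mg are in fact intended, the text should say so and the rationale section should justify them.

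The sponsor may also look at whether 10% is the right step for a level of 0.51-1.00 IU/mL in children on a full (to 30 kg) or partial (30 to 60 kg) doubling. That is left to clinical judgement.
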